Study Drug	Nitrous oxide (laughing gas). This is an FDA-approved general anesthetic and sedative agent used in hospitals and dentist offices. The use of nitrous oxide to treat bipolar depression is off-label and outside of the approved indication. Nitrous oxide will be administered under supervision of an attending-level anesthesiologist and according to standards set by the American Society of Anesthesiologists.
Intervention	Patients will receive a titrated mix of either 50% nitrous oxide/50% oxygen or "placebo" (50% nitrogen [inert]/50% oxygen) for 1 hour.
Study Design	Prospective, randomized, placebo-controlled trial using the Sequential Parallel Comparison Design. In the first stage , patients will receive 3 randomized 1-hour treatments of either nitrous oxide (25% patients) or placebo (nitrogen in air; 75% patients) every other day (e.g., M,W,F). In the second stage , participants assigned to placebo in Stage 1 will be randomized to three 1-hour treatments every other day (e.g., M,W,F) for one week, to either nitrous oxide (50% patients) or placebo (50% patients). Participants assigned to nitrous oxide in Stage 1 will remain on nitrous oxide in Stage 2. Assessments will be performed prior to each treatment series (baseline) and approximately 24 hours after inhalation sessions #1 and #2, and approximately 72 hours after inhalation session #3. One and two week assessments of continued efficacy will be made for exploratory evaluation, but not included in the primary efficacy analysis.

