7.1. Follow-Up

Assessments will be performed before and after (approximately 1 and 24 hours) each treatment, with the exception of the 3rd inhalation treatments in each Stage which will be monitored at approximately 72 hours from last inhalation session. Additional follow-up visits will be scheduled approximately one and two weeks following completion of the final gas inhalation session in any study stage (to assess for lasting efficacy of nitrous effects). However, only the two 24 hour and one 72 hour measures will be used in the statistical analysis of efficacy. The one and two week assessments will be performed to obtain preliminary information regarding lasting efficacy.

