7.2. Assessment of Treatment Efficacy

The effects of the treatment will be assessed using standard scales used for mood assessments in psychiatry, psychosis, and disassociation:

- a) the MADRS (**Primary Outcome**) to assess change in depression;
- b) the Hamilton Depression Rating Scale-17 item (Ham-D17), secondary measure of depression;
- c) Young Mania Rating Scale (YMRS) to assess emergence of mania/hypomania (patients with YMRS scores > 12 will be removed from the trial and recommended for follow-up treatment per Psychiatry P.I., i.e., nitrous oxide treatments discontinued);
- d) the Profile of Mood States, 2nd edition (POMS 2) to assess for rapid/instantaneous changes in mood/affect;
- e) the Quick Inventory of Depressive Symptomatology- Self Report (QIDS –SR) patient-rated depression measure;
- f) Clinician Administered Dissociative States Scale (CADSS) for emergence of disassociation;
- g) the Brief Psychiatric Rating Scale (BPRS) to assess psychotic or hallucinogenic behavior; and
- h) Scale for Suicidal Ideation (SSI) to assesses for emergence of suicidal thinking.

Patients will be assessed approximately 30 minutes before treatment, and approximately 1 hour and 24-72 hours after treatment by one of the expert psychiatry study team members who will be blinded to the study group assignment.

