The primary outcome variable is the change from baseline in MADRS scores during the first study week in each Stage of the SPCD study. Stage-wise test statistics representing the active vs. placebo response will be combined with equal weights for each Stage. The full analysis set is defined as all patients who were randomized and had at least one treatment dose as well as one post-baseline efficacy assessment in Stage 1. In Stage 2, the placebo non-responders who were re-randomized and had at least one treatment dose as well as one post-baseline efficacy assessment contribute to the full analysis set. A mixed model for repeated measurements (MMRM) with an unstructured variance-covariance matrix will be used for the primary efficacy analysis. This direct likelihood model is the missing data handling method recommended by the National Research Council of the National Academies of Science report on prevention and handling of missing data.

Secondary outcomes, expressed as change from baseline at 72 hours after the 3rd and final inhalation treatment will also be evaluated using the data from the full analysis set, consisting of all-comer participants from **Stage 1** and placebo non-responders in **Stage 2**. The secondary efficacy endpoints include changes in Ham-D17, Young Mania Rating Scale (YMRS), POMS, 2nd edition, and QIDS – SR. Intra- and inter-individual comparison of scores on depression scales will be done using a repeated-measures mixed effects model.

Based on our pilot study where we saw a significant reduction in depression scores among 20 unipolar depressed patients, we decided to enroll 64 patients in this trial which is similar (or larger) than previous studies of rapid antidepressants in this patient population.

10. Risk Assessment

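### YMRS is collected to detect emergent mania, but its only stated analysis is a 72-hour efficacy change in a set that omits the Stage 2 data of the 16 patients continuing nitrous oxide; no by-arm summary in all treated patients is planned

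*Combined protocol and SAP*

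**What the plan says.** Section 7.2(c) gives the YMRS a safety purpose: to pick up mania or hypomania that emerges on study. A score above 12 leads to removal. Tolerability is the second of the two specific aims (Section 1.2).

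Section 9 lists the scale among efficacy measures: "The secondary efficacy endpoints include changes in Ham-D17, Young Mania Rating Scale (YMRS), POMS". These outcomes are "expressed as change from baseline at 72 hours after the 3rd and final inhalation treatment" and use the full analysis set. In Stage 1 that set takes all randomised patients with at least one dose and one post-baseline efficacy assessment. In Stage 2 the contributors are "the placebo non-responders who were re-randomized and had at least one treatment dose" and a post-baseline efficacy assessment.

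Section 7.1 adds that "only the two 24 hour and one 72 hour measures will be used in the statistical analysis of efficacy", without naming a scale. Section 9 describes the model for these outcomes as "Intra- and inter-individual comparison of scores on depression scales will be done using a repeated-measures mixed effects model", and the YMRS is not a depression scale. It is therefore open whether the 24-hour YMRS values enter.

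Section 7.3 says how psychiatric and other adverse events are identified; its examples are psychosis and suicidality. Section 8.2 sends serious or unexpected events to the DSMB. No section defines a safety population, an adverse event table, or a count of YMRS above 12 by arm.

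**The concern.** The purpose of the scale and its analysis do not match, in three ways.

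- **Measure.** Emergent mania is an event in an individual. A mean change three days after the last session is not an incidence. As an illustration, one patient among 16 who rises by 12 points moves the arm mean by 12/16 = 0.75 points.
- **Population.** The Stage 2 restriction suits the efficacy contrast of a sequential parallel comparison design. It does not suit tolerability, because it discards second-stage data from patients who are receiving the drug.
- **Missing values.** Patients removed for a high YMRS before the 72-hour visit may not contribute to the 72-hour endpoint, so the analysis can miss the cases that the scale is there to find.

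This matters because Section 10.2 describes the trial as the first of nitrous oxide in bipolar depression, and the pilot in Section 2 was in 20 unipolar patients. Section 2 names triggering of mania as a drawback of ketamine in bipolar patients, and Sections 3 and 10.1 list euphoria as an effect of nitrous oxide. The stake is how well Aim 1.2 is answered for the harm most specific to this condition.

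**Working it through.** **Inputs.** 64 patients (Section 5); 1:3 nitrous oxide to placebo in Stage 1; all Stage 1 placebo patients re-randomised 1:1; Stage 1 nitrous oxide patients continue on it (Sections 6.1 and 6.2); three sessions per Stage. Full retention is assumed. The open-label option is not counted.

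**1. The plan's own figure.** 64 × 3/4 = 48 on placebo in Stage 1, which agrees with the approximate 48 in Section 6.1. Hence 64 × 1/4 = 16 on nitrous oxide, and 48/2 = 24 per re-randomised arm in Stage 2.

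**2. Blinded nitrous oxide exposure.** Patients: 16 + 24 = 40. Sessions: 16 × 6 + 24 × 3 = 96 + 72 = 168. Only the 16 continuing patients have a fourth to sixth nitrous oxide session.

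**3. What falls outside the analysis set.** The 16 continuing patients are in the set for Stage 1 but not for Stage 2, so 16 × 3 = 48 sessions are outside, and 48/168 = 28.6%. If a proportion r of placebo patients respond in Stage 1, split equally between the Stage 2 arms, the sessions outside number 48 + 72r and the Stage 2 nitrous oxide patients inside number 24(1 − r) of 40. The documents give no response rate, so r is assumed.

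| r (assumed) | Sessions outside, of 168 | Stage 2 nitrous oxide patients inside, of 40 |
|---|---|---|
| 0 | 48 (29%) | 24 (60%) |
| 0.2 | 62.4 (37%) | 19.2 (48%) |
| 0.4 | 76.8 (46%) | 14.4 (36%) |

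**4. What an all-treated table could show.** With zero events in n patients, the upper limit of the exact two-sided 95% interval is 1 − 0.025^(1/n): 20.6% for n = 16, 14.2% for 24, 8.8% for 40 and 7.4% for 48. The documents give no rate for YMRS above 12. At an assumed per-patient rate p, the chance of at least one event is 1 − (1 − p)^n. For p = 5% this is 0.56 with n = 16 and 0.87 with n = 40; for p = 10% it is 0.81 and 0.99.

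**5. Whether the arms could be tested.** With a two-sided Fisher test at 0.05 and assumed rates of 10% against 1% or 2%, power is 0.20 or 0.17 for 16 vs 48, and 0.07 or 0.05 for 24 vs 24. The table can only be descriptive.

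**The case against.** The strongest reply is that tolerability is not neglected. Section 7.2 makes a high YMRS a removal event, Section 7.3 collects psychiatric, cardiovascular, respiratory and other events, Section 8.1 refers to procedures for adverse event reporting that are not reproduced, and Section 8.2 sets up a full DSMB. Aim 1.2 promises data, not a test. This is right as far as it goes. A reader might infer that mania is not monitored, or that the trial would yield no tolerability data; the documents support neither. Monitoring is not a planned summary, however. Without one, the population and visits would be chosen after the data are seen, even though Section 7.2 already fixes a threshold.

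A second reply is that Section 7.2 explains removal as stopping the gas treatments, so ratings may continue. That stands: loss of the 72-hour value is possible, not shown.

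A third is that three time points per Stage may be used for the YMRS, because Section 7.1 admits the 24-hour values. That is a natural reading. It does not change the population or turn a mean change into an incidence.

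It is also tempting to say that the 1-hour ratings go unused, or that POMS 2 is analysed at the wrong time. Section 7.1 limits the time points for efficacy only, and a figure not shown may hold the schedule of scales by visit. The point does not rest on either.

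**Conclusion.** The point holds as a gap in the safety analysis that should be closed; the primary efficacy conclusion is not affected. Followed as written, the one stated YMRS analysis omits 29% of planned blinded nitrous oxide sessions even if no placebo patient responds, and 37% to 46% if 20% to 40% do. It covers no fourth-to-sixth nitrous oxide exposure, and it may lack values from patients removed for mania. The session counts rest on planned numbers with full retention; the higher shares rest on assumed response rates.

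Two stronger readings should be avoided. The 16 continuing patients are not excluded altogether, because their Stage 1 data are analysed. Nor is the full analysis set wrong for efficacy; it is only unsuited to tolerability.

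**What to change.** Leave the efficacy set and the removal rule unchanged. Add to Section 9 a descriptive safety summary in all patients who receive at least one session, by treatment received. Give the number and proportion with YMRS above 12 at any assessment after the first dose of that Stage, and the number removed for it, with exact two-sided 95% intervals. Show baseline YMRS alongside, because the entry criteria set no YMRS limit and pre-existing elevation should not be counted as emergent. The rows would be:

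- Stage 1: 16 vs 48.
- Stage 2, re-randomised regardless of response: 24 vs 24.
- Stage 2, continuing nitrous oxide: 16, with no randomised comparator.
- All patients exposed to blinded nitrous oxide: 40.

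Note that the Stage 2 rows are conditional on completing Stage 1. Keep the 72-hour YMRS change as supportive, and say whether the 24-hour values enter its model. Reconcile the two descriptions of removal in Section 7.2(c), leaving the trial and stopping the gas treatments, so that it is clear whether ratings continue.

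The cost is some plan wording and a few tables, using YMRS ratings that the protocol already collects. The intervals will be wide, and the tables cannot support a comparison between arms.

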10.1. Nitrous oxide

The side effects of nitrous oxide are well known to anesthesiologists. The dose (50%) and duration (1 hour) used in this protocol are considered very safe and low risk. Similar doses and durations are used in everyday dental practice without vital sign monitoring or supervision by a resuscitation-trained physician. With this dose of nitrous oxide, sedation may occur but not general anesthesia or respiratory depression. Minor side effects after nitrous oxide exposure such as nausea and vomiting may occur (and were observed in our preliminary study in unipolar depression), which are typically

self-limited and short. If a patient develops moderate to severe nausea and vomiting, we may administer 4mg of ondansetron. Other risks include euphoria, anxiety and increased heart rate.

10.2. Major depression and suicide risk

Because this is a first in-human study of nitrous oxide in the treatment of bipolar depression, a worsening of depression symptoms and an increased risk for suicide cannot a priori be excluded. After each treatment, an expert research team member and, if needed, psychiatrist will determine the suicide risk and if indicated, take the necessary precautions to mitigate this risk including recommendation of treatment, hospitalization and withdrawal of subject from the study to preserve safety.

11. References

- 2. Hirschfeld RM, Vornik LA (2004): Recognition and diagnosis of bipolar disorder. *J Clin Psychiatry*. 65 Suppl 15:5-9.
- 6. Sidor MM, Macqueen GM (2011): Antidepressants for the acute treatment of bipolar depression: a systematic review and meta-analysis. *J Clin Psychiatry*. 72:156-167.
